# + info: http://capenergy.com/es/product-detail/

The treatment will consist of the application of diathermy, providing the effects of tecartherapy, which are perceived as endogenous heat on the treated area.

The treatment will be individual and exclusive, with maximum discretion, in a quiet and relaxed environment.

The duration of the treatment will be 5 weeks, where 10 sessions will be carried out, 2 per week.

The cost of the treatment is valued at 1000 euros. Participants agree to start and end the study. In case of abandonment, they must reimburse the cost of the treatment.

The cost of the tests carried out will not be passed on to the patients, it is valued at 212 euros.

On the part of the professionals of INNEOTERAPIA, the treatment protocol established in the study will be applied.

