## [1] Sample size. Comparison for paired means.

Data:

Mean differences to be detected:	6.442
Standard Deviation of the differences:	8.221
Level of confidence:	95.0%
sults.	

Results:

Stat. Power (%)	Number of Pairs
80.0	15

Inclusion criteria:

- Men and women from 20 to 60 years old

- With Waist-Hip Index. Greater than: 0.84 normal for women. 94 normal for men.

- Body Mass Index that is defined as: Overweight: Between 25-29.9. Obesity: 30 or higher.

- Measurement of Visceral Fat per Inbody greater than 9, which is what is considered Normal.

- Signed informed consent (Annex 1).

Exclusion Criteria:

- Contraindication to the use of radiofrequency: pregnancy, metal prostheses, active infection.

- Patients with a history of cancer, chemotherapy and radiotherapy treatments.

- Not having diabetes or metabolic disease.

MEASUREMENTS

Body Mass Index, Waist-t-Hip ratio and visceral fat:

Body Mass Index is calculated as follows: Body Weight (Kg) ÷ (Height in cm)2

Waist-to-Hip Ratio: According to World Health Organization guidelines, the waist should be measured at the midpoint between the last palpable rib and the top of the iliac crest (upper edge of the pelvis). The hip should be measured at the point of maximum circumference, i.e. the point where the buttocks reach maximum width. Both measures should be taken immediately after the air in the lungs is exhaled. It is important to keep your feet together and your arms in a normal position next to your body. It is advisable to take each measure twice and repeat it if different results are obtained (WHO 2008). The caliper takes the thickness of the abdominal wall at 5 cm in an oblique line towards the navel on the right and left side.

The visceral fat value: will be measured using, in addition to the MRI method, an Inbody electrical impedance equipment, in the first and last session.

TREATMENT

Each patient will have 4 active, automatic plates placed on the abdomen, two on the right side of the midline and two on the left side. Energy will be applied for 50 minutes, controlling the temperature. Subsequently, 15 minutes of Capacitive and Resistive manual electrodes will be applied to the abdomen, simultaneously, 20 minutes of Lymphatic Drainage placing one active plate in the foot and the other in the lumbo-dorsal area. You will be informed that you will only feel comfortable warmth. Five sessions will be applied from Monday to Friday resting Saturday and Sunday, for 2 weeks. Total 10 sessions.

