# **STUDY PROTOCOL**

The study will be carried out to 20 candidates who want to participate free of charge in exchange for their testimony and their commitment to the study.

The treatment will be carried out with the only technology on the market from Capernergy Medical, with its C-400 equipment, approved and authorized by the Ministry of Health, with its own national and international patents.

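### Participants who leave the study must repay a treatment valued at 1000 euros, with no visible exception for discomfort, adverse effects or medical reasons

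*Combined protocol and SAP*

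**What the plan says.** The Study Protocol part says 20 candidates may "participate free of charge in exchange for their testimony and their commitment to the study". The section after it, which follows the manufacturer's product link, gives the price: "The cost of the treatment is valued at 1000 euros". The next two sentences set the obligation: "Participants agree to start and end the study. In case of abandonment, they must reimburse the cost of the treatment". Test costs are handled differently: "The cost of the tests carried out will not be passed on to the patients, it is valued at 212 euros".

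That section describes the treatment as "perceived as endogenous heat on the treated area". On exposure, the Treatment text in the Methodology states "Energy will be applied for 50 minutes, controlling the temperature", and the Brief Description repeats the 50 minutes. The same Treatment text says participants will be told to expect nothing beyond a pleasant warmth.

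The Methodology provides for an information sheet and signed consent (Annex 1) and says the project will go to a university ethics committee. The available text contains no statement on the right to withdraw.

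**The concern.** A participant's freedom to leave should not depend on ability to pay. Here completion is free and departure carries a bill, so anyone who wants to stop has a financial reason to go on with a heat treatment. Those most exposed are the participants for whom the promise of pleasant warmth proves untrue.

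The data could be affected too. Retention obtained by a charge makes the treatment look better tolerated than it is. Participants might also play down discomfort, but this is only an inference: the clause charges for leaving, not for reporting, and staff giving individual sessions may notice a problem. The documents give no dropout or adverse-event rate, so neither effect can be sized.

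**Working it through.** The point rests on reading the text; the arithmetic only sets its scale.

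**The passages side by side**

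1. Participation is free in exchange for, among other things, commitment to the study (Study Protocol).
2. The treatment is valued at 1000 euros, participants undertake to finish, and leaving triggers reimbursement (next section). The duty is mandatory, and the amount is the cost of the treatment as a whole.
3. Test costs, 212 euros, are expressly not charged to participants. The section thus considers who bears which cost, and gives the treatment cost no such protection.
4. No available text defines abandonment, exempts any reason for leaving, or scales the charge to the sessions received.

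**Charge for leaving after session k**

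Inputs: 1000 euros; 10 sessions, from "Total 10 sessions" in the Treatment text and from "The duration of the treatment will be 5 weeks, where 10 sessions will be carried out, 2 per week" in the Study Protocol part; 50 minutes of plate heating per session.

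- Literal reading: 1000 euros at any k.
- Pro-rata reading (an assumption; the text does not say it): 1000 / 10 = 100 euros per session received, so 100 × k.
- Plate heating still to be completed to avoid the charge: (10 − k) × 50 minutes.

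| Leaving after session | Literal charge (euros) | Pro-rata charge (euros) | Heating still to complete (minutes) |
|---|---|---|---|
| 0 | 1000 | 0 | 500 |
| 1 | 1000 | 100 | 450 |
| 5 | 1000 | 500 | 250 |
| 10 (finished) | 0 | 0 | 0 |

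The Treatment text spreads the sessions over 2 weeks and the Study Protocol part over 5. That contradiction must be reconciled, but both give 10 sessions, so the minutes do not change. Manual-electrode and drainage times are left out because the Brief Description and the Treatment text disagree on them.

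**Room for losses**

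The sample-size table gives 15 pairs, from a mean difference of 6.442, an SD of differences of 8.221, 95% confidence and 80% power. A two-sided paired t-test using the noncentral t distribution reproduces this: n = 15, power 0.806. (The normal approximation gives 13.) With 20 candidates, 20 − 15 = 5 losses (5/20 = 25%) would still leave the plan's own number, although the documents do not call the extra 5 a dropout allowance.

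This margin holds only for the tabulated inputs. The accompanying text names a difference of 2, an SD of 8.0 and a correlation of 0.70. These give an SD of differences of 8 × √(2 × 0.30) = 6.20 and 78 pairs. That discrepancy is a separate matter; neither figure justifies charging people who leave.

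**The case against.** The strongest objection is that the absence of an exception is an absence from the text available here. Annex 1 and the consent pages were not in it, and a right to withdraw would normally be stated there. This stands as a limit: one can say that no exception is visible, not that none exists. It does not rescue the sentence, because an unqualified duty to pay would contradict a consent form that allows free withdrawal.

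Second, abandonment is undefined. A stop ordered by staff or forced by an adverse effect might not count. That is a fair reading, and it means one cannot say the charge certainly applies to every departure. But the text does not settle the matter, and a participant deciding whether to stop cannot know. A narrower definition would still charge someone who simply finds the heat unpleasant.

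Third, free participation was conditional on commitment from the start, so the clause spells out that condition and does not contradict the offer. This is correct; the objection to the clause is what it does, not that it is inconsistent with the offer.

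Fourth, an ethics committee will see the project, and the Introduction describes the method as well tolerated with almost no side effects. The committee may well remove the clause, but the documents do not show that it has. Good tolerability reduces how many people are affected, not what the clause does to each person it catches.

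Finally, the minute counts measure exposure, not harm or coercion. That is accepted; they show only what a participant would have to complete to avoid the charge.

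**Conclusion.** The concern holds and must be fixed. As written, finishing costs 0 euros and leaving costs 1000 euros on the literal reading. With no pro-rata rule stated, the possible range for a partial course is 0 to 1000 euros. No visible text exempts discomfort, adverse effects or medical reasons.

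Confidence is high that the clause exists and needs correcting whatever Annex 1 says. Three things cannot be determined from the documents: whether Annex 1 contains an exception, how many participants would be affected, and how far retention or tolerability data would be distorted. The conclusion depends on none of them.

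**What to change.** In the Study Protocol part, delete the sentence requiring reimbursement on abandonment and reword the undertaking to start and end the study so that it does not read as an obligation to stay. State instead that participants may withdraw at any time, for any reason, at no cost. Make the information sheet and consent form (Annex 1) say the same.

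To protect the data by other means, record the date and reason of each withdrawal and invite those who leave to the final measurements already planned, with attendance voluntary.

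**Cost.** The text change is small: this passage and matching wording in Annex 1. The site gives up at most 1000 euros per withdrawal: up to 1000 to 5000 euros for an assumed 1 to 5 withdrawals, and 20 × 1000 = 20,000 euros in the extreme case that all 20 leave. A few more people may withdraw, and each one without a final measurement removes 1/20 = 5% of the candidates from the before/after comparison; more than 5 such losses would take the study below its stated 15 pairs. The cost of measuring those who leave cannot be fixed, because the 212 euros is not tied to particular tests, time points or a single participant. Since final measurements were planned anyway, the addition may be small.

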# Candidates are required to meet a number of criteria:

- Candidates are required to meet a number of criteria:
- Body mass index > 25.0
- CC value > 80cm for women and > 94cm for men
- Non-pregnant people, metal prostheses, suffering from bacterial infection, with a history of oncological, with chemotherapy or radiotherapy treatments.
- Commit to following a diet and physical exercise pattern for the duration of the treatment, of which they will be informed on the first day of assessment.

# **Objective of the study:**

- 🛠 Main
  - Decrease in body fat and biochemical markers.
- Secondary
  - Reduction in abdominal fat.
  - Decrease in abdominal circumference, body mass index.
  - Changes in glycemia, cholesterol and triglycerides.
  - Evaluate and compare the impact of quality of life.

#### National Identification Number:

The maximum temperature reached and the exposure time would be relevant factors to understand the response of the tissues to the increase in temperature. Goldberg, Fazeli and Berlin used a protocol with temperatures of 40-42 °C in the epidermis, not to mention the time spent at this temperature (Golberg et al 2008). Van Der Lugt et al in 2009, observed lysis of the adipocyte membrane after RF application. The authors used equipment with variable frequency (0.6-2.4 MHz) appropriate to the temperature of the tissues. Moving in a frequency range is advantageous, as tissues have different impedances, this decreases with increasing temperature, and by adjusting the frequency, a certain temperature can be maintained in a target tissue longer or with greater control, depending on the depth (van der Lugt et al, 2009). That is, according to van Der Lugt et, a temperature in the epidermis of 42 to 44 °C is equivalent to a temperature of 45 to 48 °C at 20 mm of depth. This difference is due to the low water content of adjocytes which increase their impedance. The authors report that at these temperatures, protein denaturation and thus adjpocyte membrane lysis occur (van der Lugt et al 2009). Cell death increases with temperature exposure (increase in temperature and duration of exposure), signaling that an exposure to 3-minute cell phone at a temperature of 45°C reaches 40% cell death (Franco et Al 2010). Radiofrequency thermal stimulation of adipose tissue is thought to result in heatmediated stimulation of adipocyte metabolism and increased lipase-mediated activity of enzymatic degradation of triglycerides into free fatty acids and glycerol that adds to the induction of fat cell apoptosis (Weiss 2013).
